- a If a patient discontinues treatment with IMP early during the Treatment Period, the patient will have a Premature EOT Visit, and a Follow-up Visit 2 weeks after the last dose of IMP. However, every effort will be made to have the patients return to the site for all scheduled visits, in particular the visits at Week 18 (Visit 12) and Week 52 (Visit 15). If the patient does not agree to a site visits, the patient will be contacted by telephone to inquire about safety status. If a patient discontinues (or completes) treatment and study at the same time, a single visit for both EOT and EOS will be performed.
- b To ensure effective Lantus dose titration during the Run-in Phase, patients will be instructed to call the Investigator to discuss the necessary adjustments in Lantus dose if they have 2 or more SMBG measurements above 100 mg/dL or below 80 mg/dL.
- c Two weeks after the last dose of IMP.
- d Height to be measured only at Screening.
- e Vital sign measurements (sitting blood pressure [BP], heart rate): 3 separate seated BP and heart rate measurements should be taken with at least 1 minute between readings, following a 5-minute rest period and prior to phlebotomy (if applicable).
- f The abbreviated physical exam should focus on cardiac and respiratory systems, as well as any areas important for assessment of AEs if necessary.
- g Fasting (pre-breakfast/pre-injection if available) SMBG: during the 4-week Run-in Lantus titration period, fasting SMBG should be performed daily. Thereafter, the number of fasting SMBG checks can be reduced according to the Investigator's judgment, however at least 3 fasting (pre-breakfast) SMBG measurements per week should be done from Weeks 0 to 18 and 3 measurements during the week prior to study visits from Weeks 19 to 52 (Section 8.2.1.4). Patients will review SMBG values with site staff either at site visits, phone visits or extemporaneously if patient feels high or low SMBG values may necessitate a dose adjustment. See Table 2 for permitted adjustments. Patients should be advised to check SMBG whenever they experience any symptoms of hypoglycemia, if possible, before taking the treatment. **Note:** Units in table represent plasma glucose values as glucometers used for SMBG display results already adjusted to plasma concentration and no conversion is required.

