2.1.3 Efficacy endpoints

All efficacy measurements collected during the study will be considered for analyses, including those obtained after IMP discontinuation or introduction of rescue therapy (see [Section 2.5.4](#)).

HbA1c, 2-hour PPG, FPG, UACR, and eGFR are measured/calculated in a central laboratory (see study flowchart in [Appendix D](#)). Body weight, SBP and DBP (see [Section 2.1.5.3](#)) are measured at on-site visits by the investigator. Patients requiring rescue are identified as those with the reason for treatment ticked “rescue therapy” in e-CRF “Medication” page or with the answer to the question “Is intended daily dose give per protocol or rescue therapy” ticked “rescue therapy” in e-CRF “Exposure-Treatment Period (Lantus)” page.

Efficacy variables will be summarized in both standard international units and conventional units when applicable.

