2.4.4.3 Analyses of other efficacy endpoints

Except for PRO endpoints, the analysis of other endpoints (see [Section 2.1.3](#)) will be descriptive with no formal testing. Summary statistics at scheduled visits will be provided by each treatment group. Graphical presentations will also be used to illustrate trends over time. For the daily Lantus dose (U) and daily Lantus dose adjusted by body weight (Lantus dose/body weight in U/Kg),

summary statistics (for screening value, run-in value, baseline value, and observed values) at scheduled visits (using OC) will also be provided for each treatment group.

The change from baseline values will be summarized for UGE and UGCR. These 2 variables have been added for analyses.

For the daily Lantus dose and total daily insulin dose, the baseline value is defined as the available value on the last day prior to the first dose of double-blind IMP for those randomized and exposed or before randomization for those who were randomized but never exposed to IMP.

The number (%) of patients achieving HbA1c response (<6.5%, <7% at Week 18, Week 26 and Week 52, respectively) will be descriptive summarized at each scheduled visit.

The number (%) of patients who used rescue therapy and a KM curve for the time to first rescue therapy will be provided by treatment group during the entire 52-week treatment period (see [Section 2.5.4](#)). A list of patients who used rescue therapy will also be provided.

UACR will be log-transformed at patient level. Summary statistics of UACR in log scale will then be calculated for each treatment group at each visit and back-transformed to provide the geometric mean and its associated percent change of UACR from baseline.

Shift tables will be provided for UACR at Week 26 and Week 52 using the pre-defined categories. That is, the number (%) of patients with progression from one category at baseline to another category at Week 26 and Week 52 will be provided by treatment group. The pre-defined categories are, for UACR, <30 mg/g creatinine [Normal], ≥30 to <300 mg/g creatinine [Microalbuminuria], and ≥300 mg/g creatinine [Macroalbuminuria].

The analysis of TRIM-D scores is in [Section 2.4.7](#).

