When a patient has more than 1 measurement from the central laboratory for the same laboratory parameter on the same date, the average of the measurements will be used. For the same laboratory parameter, if a patient has more than 1 measurement on different dates for the same

scheduled visit, the value closest to the date of the visit will be used for the scheduled visit. When the values for the same scheduled visit are equidistant, the last value should be used for the scheduled visit. Similar rules will be applicable to a patient who has more than 1 set of measurements for the same vital sign parameter (ie, SBP, DBP, or HR) on the same date.

Time to event analysis

For time to event analysis/KM plot, time to event (eg, treatment discontinuation, rescue therapy, hypoglycemia, etc) is defined as the number of days from the date of the first administration of double-blind IMP (or the date of randomization if not exposed) to the start date of the first occurrence of the event during entire 52-week double-blind treatment period.

Patients who did not experience any event during the entire 52-week double-blind treatment period are considered censored observations. For treatment discontinuation and time to rescue, censoring date is the date of EOT. For time to severe or documented hypoglycemia, censoring date is date of EOT+1 or date of EOS, whichever is the earliest. Date of EOS will be used if date of EOT is not available. Last contact date will be used if date of EOS is not available.

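### SAP 2.5.4 counts rescue over 52 weeks but censors event-free patients at end of treatment, so the rescue Kaplan-Meier curve, read literally, can only be right or too high

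*SAP*

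**What the plan says.** The time-to-event rules are in SAP 2.5.4. Time runs from first double-blind IMP to the "start date of the first occurrence of the event during entire 52-week double-blind treatment period". On who is censored: "Patients who did not experience any event during the entire 52-week double-blind treatment period are considered censored observations". On when: "For treatment discontinuation and time to rescue, censoring date is the date of EOT". The end-of-study date, and then last contact, are used only if the preceding date is not available.

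SAP 2.4.4.3 asks for the number (%) of patients rescued and "a KM curve for the time to first rescue therapy will be provided by treatment group during the entire 52-week treatment period". SAP 2.1.3 says how rescue is found: "Patients requiring rescue are identified as those with the reason for treatment ticked" as rescue therapy on the Medication page, or by a matching tick on the Lantus exposure page. Neither route carries an IMP-date condition. The same section says: "All efficacy measurements collected during the study will be considered for analyses, including those obtained after IMP discontinuation or introduction of rescue therapy".

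IMP can end before the period does. Footnote a of the Protocol 1.2 flow chart begins "If a patient discontinues treatment with IMP early during the Treatment Period" and gives such a patient a premature EOT visit, while asking that the scheduled visits still be attended. Protocol 10.3.4 says the same of later visits, and Protocol 9.1.4.7 has rescue use reported throughout the Treatment Period.

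**The concern.** A Kaplan-Meier risk set must be decided by what has happened up to each time point. Here, whether an early IMP stopper is censored depends on the rest of the 52 weeks, but the censoring time is then set back to EOT. Someone who stops at Week 20 and is rescued at Week 35 counts as at risk until Week 35. Someone who stops at Week 20 and is never rescued disappears at Week 20. Event-free time after EOT is discarded, while events after EOT are kept.

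The proportion needing rescue over 52 weeks is a named efficacy endpoint (Protocol 9.1.3, SAP 2.1.3.3), and this curve is its time-to-event display. A curve built this way can disagree with the n (%) reported beside it for a reason unrelated to loss to follow-up.

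**Working it through.** There is no plan figure to reproduce: the documents state no rescue rate, IMP discontinuation rate or Kaplan-Meier value.

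**1. Which window does the text set?**
- SAP 2.2 counts patients who stopped IMP during the 52-week double-blind period, so that period is not simply time on drug.
- SAP 2.1.4 has its own term for time on drug, the treatment epoch. The rescue rule does not use it.
- In SAP 2.4.5.1 the hypoglycemia curve is expressly limited to the TEAE period, and 2.5.4 censors it at EOT+1 (or end of study if earlier). Its window and its censoring match. The rescue curve has no such limit.

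**2. Direction.** Compare the rule as written with censoring at the end of each patient's 52-week follow-up. At every event time the number of events d is the same, and the number at risk n is equal or smaller under the SAP rule. Each factor (1 − d/n) is therefore equal or smaller, and 1−KM is equal or larger. It is strictly larger whenever a rescue follows the EOT of an early stopper who was followed on and never rescued. In 2,000 simulated arms of 140 (cumulative hazards over 52 weeks of 0.2 for stopping IMP and 0.25 for rescue, the latter unchanged after IMP), the SAP rule was never lower and always higher.

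**3. An arm that can be checked by hand (invented numbers, n = 140).** 28 patients stop IMP at day 126; 6 of them are rescued at day 250 and 22 never. The other 112 stay on IMP, and 22 of them are rescued at day 300.
- Crude proportion: (6 + 22)/140 = 20.0%.
- SAP rule: the 22 leave at day 126, so 118 are at risk at day 250 and 112 at day 300. 1 − (112/118)(90/112) = 1 − 90/118 = 23.7%.
- Censoring at day 364: 1 − (134/140)(112/134) = 1 − 112/140 = 20.0%.
- Consistent on-IMP curve (events and censoring both end at EOT): 22/112 = 19.6%.

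The literal rule gives a figure above both coherent alternatives.

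**4. Size under assumed rates.** Simulation of 1,000,000 patients per scenario, exponential times, every IMP stopper followed to Week 52. Entries are 1−KM under the SAP rule minus the true 52-week proportion, in percentage points. Ranges run over a post-IMP rescue hazard of 0.5, 1 or 2 times the on-IMP hazard.

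| Stop IMP by Week 52 | On-IMP rescue risk 10% | 20% | 30% |
|---|---|---|---|
| 5% | 0.23–0.24 | 0.38–0.46 | 0.47–0.64 |
| 10% | 0.49–0.50 | 0.82–0.94 | 0.99–1.31 |
| 15% | 0.78–0.79 | 1.31–1.45 | 1.58–2.03 |
| 20% | 1.06–1.14 | 1.86–1.99 | 2.23–2.77 |
| 30% | 1.70–2.01 | 3.19–3.26 | 3.80–4.42 |

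Example: 20% stopping, 20% risk, hazard unchanged after IMP. The SAP rule gives 22.0%; censoring at day 364 gives 20.0%.

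**5. Against sampling error.** At 30% risk the binomial SE is √(0.3 × 0.7/140) = 3.9 points in an arm of 140 and √(0.3 × 0.7/280) = 2.7 points in the 400 mg arm. In an arm of 140 the excess stays below one SE up to 20% stopping (at most 2.8 points). It passes one SE only in the bottom right cell of the table (4.4 points at its upper end).

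**The case against.** The strongest reply is that the 52-week double-blind period is never defined, and that for this curve it may have been meant to end at EOT. One sentence in SAP 2.5.4 sets the event window for treatment discontinuation, rescue and hypoglycemia together. The first is on-IMP by nature, and the third is tied to the TEAE period elsewhere. Choosing EOT as the censoring date is itself a sign that observation was meant to stop there. The statement in SAP 2.1.3 about data after IMP discontinuation concerns measurements and refers to 2.5.4, and SAP 2.4.4 allows for exceptions. On that reading the curve is a consistent on-IMP curve and the bias disappears.

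Rescue recorded after IMP may also be rare. Protocol 8.2.4 describes rescue with IMP continuing. Protocol 8.7.2 has study Lantus returned at the final on-treatment visit, which would largely end the Lantus-page tick. Patients who leave treatment and study together have no time after EOT and add no bias; the simulation contains none of them, so it errs towards the larger size.

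Much of this stands. That rescue after IMP is counted is an inference from the event window, not something the SAP states, and the size is unknown. It does not remove the mismatch: the text that defines who is censored looks across all 52 weeks, and the SAP's own on-drug terms are absent from the rescue rule. A programmer following 2.5.4 as written would build the inconsistent risk set.

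**Conclusion.** The mismatch is in the text. If SAP 2.5.4 is followed literally, the rescue curve can only equal or exceed the 52-week proportion. The excess is about 0.2 to 4.4 points under the assumed rates (5–30% stopping IMP, 10–30% rescue risk, complete follow-up after IMP). If no rescue is recorded after IMP, the mismatch adds nothing and the curve is an ordinary on-IMP curve. The crude n (%) over 52 weeks is not affected.

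The point is minor. Rescue is a descriptive endpoint outside the testing hierarchy (SAP 2.4.4.3 and 2.4.4.4), and SAP Appendix C lists summary statistics as its primary analysis and the KM plot under other analyses.

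A reader might infer more than the documents support:
- *That the comparison between arms is distorted.* Discontinuation and rescue may differ by arm, but no rates are given, and any error is upward in every arm. A distortion is possible, not shown.
- *That on the EOT-limited reading the n (%) would be too low.* That presumes a target that counts rescue regardless of IMP, which the SAP never states for this analysis.
- *That any gap between curve and n (%) proves the error.* With study dropout, a correctly censored curve can also differ from the crude proportion.

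**What to change.** State one window in SAP 2.5.4 for both events and censoring. To match the protocol's 52-week rescue endpoint, censor event-free patients at the earlier of the Week 52 visit (Day 364 if missing) and end of study or last contact, and count rescue over the same interval in the n (%) and the curve. EOT censoring can stay for treatment discontinuation. If an on-IMP curve is what is wanted, stop events as well as censoring at EOT and say so in the title.

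The cost is a sentence or two of SAP text and one change to a derived date. No new data are needed, because the protocol already collects rescue use and visits after IMP is stopped.

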2.5.5 Unscheduled visits

Unscheduled visit measurements of laboratory data, vital signs, and ECG will be used for computation of baseline, the last on-treatment value, PCSAs, and the shift summaries for safety or efficacy. They will be included in the by-visit summaries if they are re-allocated to scheduled visits (see [Section 2.5.4](#)).

2.5.6 Pooling of centers for statistical analyses

Center will not be included in the statistical models for efficacy analyses. However, all centers within a country will be pooled, and country will be included as a fixed effect in a parametric statistical model (eg, ANCOVA, etc) for primary and secondary efficacy endpoints. Countries with fewer than 5 randomized patients will be grouped, if patients from grouped countries are still fewer than 5, they will then be further grouped with the country with the lowest number of patients that is 5 or more.

2.5.7 Statistical technical issues

None

3 INTERIM ANALYSIS

No formal interim analysis for efficacy is planned for this study. The study will not be terminated early for excellent efficacy.

An independent Data Monitoring Committee (DMC) will be used to monitor and assess the safety of patients from this trial through periodic review of the accumulated safety data provided by an independent statistical group. Related details are provided in separate documents (DMC charter and DMC SAP).

4 DATABASE LOCK

The database is planned to be locked approximately 4 weeks after the last patient last visit.

5 SOFTWARE DOCUMENTATION

All summaries and statistical analyses will be generated using SAS[®] version 9.2 or higher.

7 LIST OF APPENDICES

- Appendix A Potentially clinically significant abnormalities criteria
- Appendix B List of PTs for select EOSIs (MedDRA v22.0)
- Appendix C Summary of statistical analyses
- Appendix D Study flow chart

Appendix A Potentially clinically significant abnormalities criteria**CRITERIA for POTENTIALLY CLINICALLY SIGNIFICANT ABNORMALITIES
for phase 2/3 studies (oncology excepted)
(From BTD-009536 May 21, 2014)**

Parameter	PCSA	Comments
Clinical Chemistry		
ALT	By distribution analysis: >3 ULN >5 ULN >10 ULN >20 ULN	Enzymes activities must be expressed in ULN, not in IU/L. Concept paper on DILI – FDA draft Guidance Oct 2007. Internal DILI WG Oct 2008. Categories are cumulative. First row is mandatory. Rows following one mentioning zero can be deleted.
AST	By distribution analysis: >3 ULN >5 ULN >10 ULN >20 ULN	Enzymes activities must be expressed in ULN, not in IU/L. Concept paper on DILI – FDA draft Guidance Oct 2007. Internal DILI WG Oct 2008. Categories are cumulative. First row is mandatory. Rows following one mentioning zero can be deleted.
Alkaline Phosphatase	>1.5 ULN	Enzymes activities must be expressed in ULN, not in IU/L. Concept paper on DILI – FDA draft Guidance Oct 2007. Internal DILI WG Oct 2008.
Total Bilirubin	>1.5 ULN >2 ULN	Must be expressed in ULN, not in $\mu\text{mol/L}$ or mg/L . Categories are cumulative. Concept paper on DILI – FDA draft Guidance Oct 2007. Internal DILI WG Oct 2008.
Conjugated Bilirubin	>35% Total Bilirubin and TBILI>1.5 ULN	Conjugated bilirubin dosed on a case-by-case basis.
ALT and Total Bilirubin	ALT>3 ULN and TBILI>2 ULN	Concept paper on DILI – FDA draft Guidance Oct 2007. Internal DILI WG Oct 2008. To be counted within a same treatment phase, whatever the interval between measurement.

CRITERIA for POTENTIALLY CLINICALLY SIGNIFICANT ABNORMALITIES
for phase 2/3 studies (oncology excepted)
(From BTD-009536 May 21, 2014)

Parameter	PCSA	Comments
CPK	>3 ULN >10 ULN	FDA Feb 2005. Am J Cardiol April 2006. Categories are cumulative. First row is mandatory. Rows following one mentioning zero can be deleted.
CLcr (mL/min) (Estimated creatinine clearance based on the Cokcroft-Gault equation)	<15 (end stage renal disease) ≥15 - <30 (severe decrease in GFR) ≥30 - < 60 (moderate decrease in GFR) ≥60 - <90 (mild decrease in GFR) ≥ 90 (normal GFR)	FDA draft Guidance 2010 Pharmacokinetics in patients with impaired renal function-study design, data analysis, and impact on dosing and labeling
eGFR (mL/min/1.73m2) (Estimate of GFR based on an MDRD equation)	<15 (end stage renal disease) ≥15 - <30 (severe decrease in GFR) ≥30 - < 60 (moderate decrease in GFR) ≥60 - <90 (mild decrease in GFR) ≥ 90 (normal GFR)	FDA draft Guidance 2010 Pharmacokinetics in patients with impaired renal function-study design, data analysis, and impact on dosing and labeling
Creatinine	≥150 µmol/L (Adults) ≥30% change from baseline ≥100% change from baseline	Benichou C., 1994.
Uric Acid Hyperuricemia Hypouricemia	>408 µmol/L <120 µmol/L	Harrison- Principles of internal Medicine 17 th Ed., 2008.
Blood Urea Nitrogen	≥17 mmol/L	
Chloride	<80 mmol/L >115 mmol/L	
Sodium	≤129 mmol/L ≥160 mmol/L	
Potassium	<3 mmol/L ≥5.5 mmol/L	FDA Feb 2005.
Total Cholesterol	≥7.74 mmol/L	Threshold for therapeutic intervention.
Triglycerides	≥4.6 mmol/L	Threshold for therapeutic intervention.
Lipasemia	≥3 ULN	

Statistical Analysis Plan

Version: Final 2.0
Lexicon Pharmaceuticals Protocol No. EFC14868

Date of Issue: 04 December 2019
Covance Study ID:000000155200

**CRITERIA for POTENTIALLY CLINICALLY SIGNIFICANT ABNORMALITIES
for phase 2/3 studies (oncology excepted)
(From BTD-009536 May 21, 2014)**

Parameter	PCSA	Comments
Amylasemia	≥3 ULN	
Glucose		
Hypoglycaemia	≤3.9 mmol/L and <LLN	ADA May 2005.
Hyperglycaemia	≥11.1 mmol/L (unfasted); ≥7 mmol/L (fasted)	ADA Jan 2008.
HbA1c	>8%	
Albumin	≤25 g/L	
CRP	>2 ULN or >10 mg/L (if ULN not provided)	FDA Sept 2005.
Hematology		
WBC	<3.0 Giga/L (Non-Black); <2.0 Giga/L (Black) ≥16.0 Giga/L	Increase in WBC: not relevant. To be interpreted only if no differential count available.
Lymphocytes	>4.0 Giga/L	
Neutrophils	<1.5 Giga/L (Non-Black); <1.0 Giga/L (Black)	International Consensus meeting on drug-induced blood cytopenias, 1991. FDA criteria.
Monocytes	>0.7 Giga/L	
Basophils	>0.1 Giga/L	
Eosinophils	>0.5 Giga/L or >ULN (if ULN≥0.5 Giga/L)	Harrison- Principles of internal Medicine 17 th Ed., 2008.
Hemoglobin	≤115 g/L (Male); ≤95 g/L (Female) ≥185 g/L (Male); ≥165 g/L (Female) Decrease from Baseline ≥20 g/L	Criteria based upon decrease from baseline are more relevant than based on absolute value. Other categories for decrease from baseline can be used (≥30 g/L, ≥40 g/L, ≥50 g/L).
Hematocrit	≤0.37 v/v (Male); ≤0.32 v/v (Female) ≥0.55 v/v (Male); ≥0.5 v/v (Female)	
RBC	≥6 Tera/L	Unless specifically required for particular drug development, the analysis is redundant with that of Hb. Otherwise, consider FDA criteria.
Platelets	<100 Giga/L ≥700 Giga/L	International Consensus meeting on drug-induced blood cytopenias, 1991.

CRITERIA for POTENTIALLY CLINICALLY SIGNIFICANT ABNORMALITIES
for phase 2/3 studies (oncology excepted)
(From BTD-009536 May 21, 2014)

Parameter	PCSA	Comments
Urinalysis		
pH	≤4.6 ≥8	
Vital signs		
HR	≤50 bpm and decrease from baseline ≥20 bpm ≥120 bpm and increase from baseline ≥20 bpm	To be applied for all positions (including missing) except STANDING.
SBP	≤95 mmHg and decrease from baseline ≥20mmHg ≥160 mmHg and increase from baseline ≥20 mmHg	To be applied for all positions (including missing) except STANDING.
DBP	≤45 mmHg and decrease from baseline ≥10 mmHg ≥110 mmHg and increase from baseline ≥10 mmHg	To be applied for all positions (including missing) except STANDING.
Orthostatic Hypotension		
Orthostatic SDB	≤-20 mmHg	
Orthostatic DBP	≤-10 mmHg	
Weight	≥5% increase from baseline ≥5% decrease from baseline	FDA Feb 2007.

CRITERIA for POTENTIALLY CLINICALLY SIGNIFICANT ABNORMALITIES
for phase 2/3 studies (oncology excepted)
(From BTD-009536 May 21, 2014)

Parameter	PCSA	Comments
ECG		Ref.: ICH E14 guidance (2005) and E14 Q&A (2012), and Cardiac Safety Research Consortium White Paper on PR and QRS (Nada et al. Am Heart J. 2013; 165(4): 489-500)
HR	<50 bpm <50 bpm and decrease from baseline \geq 20 bpm <40 bpm <40 bpm and decrease from baseline \geq 20 bpm <30 bpm <30 bpm and decrease from baseline \geq 20 bpm >90 bpm >90 bpm and increase from baseline \geq 20bpm >100 bpm >100 bpm and increase from baseline \geq 20bpm >120 bpm >120 bpm and increase from baseline \geq 20 bpm	Categories are cumulative Categories are cumulative
PR	>200 ms >200 ms and increase from baseline \geq 25% > 220 ms >220 ms and increase from baseline \geq 25% > 240 ms > 240 ms and increase from baseline \geq 25%	Categories are cumulative
QRS	>110 ms >110 msec and increase from baseline \geq 25% >120 ms >120 ms and increase from baseline \geq 25%	Categories are cumulative
QT	>500 ms	

CRITERIA for POTENTIALLY CLINICALLY SIGNIFICANT ABNORMALITIES
for phase 2/3 studies (oncology excepted)
(From BTD-009536 May 21, 2014)

Parameter	PCSA	Comments
QTc	Absolute values (ms)	To be applied to any kind of QT correction formula. Absolute values categories are cumulative
	>450 ms	
	>480 ms	QTc >480 ms and Δ QTc>60 ms are the 2 PCSA categories to be identified in individual subjects/patients listings.
	>500 ms	
	Increase from baseline	
	Increase from baseline]30-60] ms	
Increase from baseline >60 ms		

Statistical Analysis Plan

Version: Final 2.0
Lexicon Pharmaceuticals Protocol No. EFC14868

Date of Issue: 04 December 2019
Covance Study ID:000000155200

